1.2 Schema

1.3 Schedule of Events (SOE)

PLEASE NOTE: This study combined Visits 2 and 3, eliminating one study visit from the Schedule of Events prior to Day 0. To avoid issues with data and protocol implementation related to renumbering all study visits, the numbering of the Day 0 through Day 168 Visits will remain unchanged (Visits 4 through 12). We eliminated the Visit 3 from the Schedule of Events.

	Screening	Enrollment and Baseline	Day 0	Day 2	Day 7	Day 14	Day 28	Day 56	Day 70	Day 84	Day 168
Study Treatment or Placebo			X								
Post-vaccine/placebo assessment				X	X	X	X				
Completion of Post-vaccine/placebo Symptom Log by the participant				X	X						
Leukapheresis		X-----X ³					X ⁴				
Lymph Node Procedure ^{5,6}		X-----X			X ----- X						
Telephone Assessment			X						X	X	
Clinical Laboratory											
CBC with Differential	X	X			X	X	X	X	X		
Screening chemistry ⁷	X										
Safety chemistries ⁸		X			X	X	X		X		
Pregnancy test ⁹	X		X								
Urine Pregnancy – POCT ¹⁰			X		X	X	X	X	X		
Coagulations Test (PT/INR/APTT)	X										
HIV Ag/Ab test ¹¹	X										
CD4+ T Cell Differential Panel	X				X	X			X		
HIV-1 RNA PCR	X				X				X		
RPR	X										
HBsAg & HCV Ab ¹²	X										
Fasting Lipid Panel	X										
Urinalysis	X								X		
Research Laboratory Assays											
HLA typing		X									
Flow cytometry sample ⁶		X-----X			X ----- X						

	Screening	Enrollment and Baseline		Day 0	Day 2	Day 7	Day 14	Day 28	Day 56	Day 70	Day 84	Day 168
Plasma and PBMC for Immunologic and Virologic Studies ¹³	X	X ^{14, 15}		X		X	X	X ^{15, 16}	X	X		

1. Visit 2 and all associated procedures (inclusive of leukapheresis) will occur within 60 days of Visit 1. If required for scheduling, the leukapheresis visit can occur separately from Visit 2 but within 60 days of Visit 1 and after the Enrollment/Baseline visit. If the leukapheresis is on a separate day, perform the safety labs, vital signs and BMI assessment at the leukapheresis visit and the Day 0 visit within 10 days of the leukapheresis.
2. Pulse (P), blood pressure (BP), respiratory rate (RR), temperature (T) (°C, oral) and weight (kg).
3. Reference Section 8.2.3
4. Reference Section 8.2.3
5. Optional Lymph Node Procedure –consenting participants will complete 2 procedures: the first between Enrollment (Visit 2) and Day 0 and the second between Day 7 and Day 21.

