5. Explore the impact of vaccination with either M3 or M4 or M3+M4 on low-level plasma viremia.	5. The proportion of participants in whom HIV-1 plasma RNA decreases from pre-vaccination (geometric mean of Day -60 and 0) to post-vaccination (geometric mean of Day 56 and 70) as measured by single copy assay.	Exploratory endpoints 5–7 examines whether MVA vaccination has an in vivo effect on persistent HIV infection.

OBJECTIVES	ENDPOINTS	JUSTIFICATION FOR ENDPOINTS
Tertiary/Exploratory		
6. Explore the impact of vaccination with either M3 or M4 or M3+M4 on cell-associated HIV RNA in CD4+ T cells. 7. Explore the impact of vaccination with either M3 or M4 or M3+M4 on total viral DNA in CD4+ T cell.	6. The proportion of participants in whom cell-associated RNA in total CD4+ T cells decreases post-vaccination (geometric mean of Day 28 and Day 56) compared to pre-vaccination (geometric mean of Day -45 and Day 30.) 7. Proportion of participants in whom total HIV DNA in total CD4+ T cells decreases post-vaccination (geometric mean of Day 28 and Day 56) compared to pre-vaccination (geometric mean of Day -45 and Day 30.)	Exploratory endpoints 5–7 examine whether MVA vaccination has an in vivo effect on persistent HIV infection.

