Screening, Enrollment, and Leukapheresis. The participant reviews and signs the informed consent (ICF). Participants meeting eligibility requirements enroll and undergo one leukapheresis procedure between Day -60 and Day 0. The leukapheresis procedure collects white blood cells allowing for completion of detailed immunologic and virologic assays with minimal blood loss. Participants have the option to consent to a lymph node FNA; participants choosing this option will complete the pre-vaccine FNA between Day -60 and Day 0 and a post-vaccine FNA between Day 7 and Day 21. The post-vaccine FNA should be collected even if the pre-vaccine collection attempt is unsuccessful.

Randomization, Study Treatment, Follow-up Assessment, and Leukapheresis.

Randomization occurs at Day 0 when a randomization identification number (RID) will be assigned. All participants receive a vaccine or placebo dose as an IM injection. Post

vaccination safety assessments occur via clinical evaluations, and lab testing/evaluations. The study will collect research assays at designated visits.

At Day 28, all participants will undergo their 2nd leukapheresis. This procedure can be completed between Day 21 through Day 35. The leukapheresis product will be used for immunologic and virologic research assays post vaccine/placebo. Participants will be followed for immunogenicity assessments through Day 70 and safety assessments through Day 168 (Week 24) following the administration of vaccine/placebo at Day 0.

Note: The post-vaccine leukapheresis must be done as close to Day 28 as possible. There may be a rare situation where the completion of the procedure in the 2-week visit window will not be possible. As soon as the study coordinator becomes aware of this scenario, they should notify the study PI (or designee) to schedule the procedure outside the study window, preferably earlier (between Days 14 and 28). If the procedure can only be done after Day 35, participants should complete the Day 28 visit with collection of a 42.5 mL ACD sample at that visit.

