6.1.2 Dosing and Administration

Dosing

All participants will receive a single vaccine/placebo administration on Day 0. Participants randomized to Arms 1 and 2 will receive 2×10^8 pfu of **M3** or **M4**, respectively.

Participants randomized to Arm 3 will receive a 1×10^8 pfu dose of both **M3** and **M4** (total dose 2×10^8 pfu **M3+M4**). Participants randomized to Arm 4 will receive placebo ([Table 7](#)).

Table 7 Arms in the Clinical Study

Arm	N	Day	Treatment	Dose (pfu)	Volume (mL)	Route
1	7	0	M3	2×10^8	.59	IM
2	7	0	M4	2×10^8	1.11	IM
3	7	0	M3+M4	1×10^8 , each vaccine	.29 + .56 (total 0.85)	IM
4	3	0	Placebo/saline	-	1.0	IM

M3 = MVA.tHIVconsV3 **M4** = MVA.tHIVconsV4 pfu = plaque forming units IM = intramuscular

For the purpose of this study and safety management, a maximum of 2 study participants will be vaccinated each week.

Study Treatment Administration

Both M3 and M4 vaccines should be thawed to room temperature and administered within 60 minutes of removal from the freezer.

The combination dose of M3 and M4 (Arm 3) will be delivered as a single injection, with both products drawn up into a single syringe for administration in IDS.

Administer all vaccines/placebo doses as a single injection at Day 0.

Administer all vaccine/placebo doses as an IM injection in the deltoid muscle of the non-dominant arm, unless a participant requests vaccination in their dominant arm.

The study DOES NOT ALLOW any modifications to any vaccine doses.

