FNA and Matching Blood Sample

Analyzed for T-cell specificity, phenotype and function, and virologic measurements per the SOE. Performance of assays is dependent on cell yield and viability. Specific testing may include the following:

- Quantification of T cell memory frequencies and activation pre- and post-treatment
- Cell-associated viral RNA in CD4⁺ T cells pre- and post-treatment

Measurements of HIV specific T cell responses pre- and post-treatment Human Leukocyte Antigen (HLA) Typing

HLA testing will be performed at one time point in the study; however, if HLA type is already available in the medical record, it does not need to be repeated. The result will be used for research purposes.

Stored Plasma/PBMC for Immunology Studies: Plasma and cryopreserved PBMC will be stored for analysis of low level viremia, T-cell specificity, phenotype and function, and virologic measurements per the SOE. Specific testing will include the following:

- Low-level HIV-1 RNA assays pre- and post-treatment
- Measurement of T cell responses pre- and post-treatment
- Measurement of T cell virus inhibition pre- and post-treatment
- Phenotyping of both total and specific CD4⁺ and CD8⁺ T cell activation, homing and memory differentiation using flow cytometry pre- and post- treatment
- Functional analysis (e.g., anti-viral cytokine and lytic molecule release) of both total and specific T cells pre- and post-treatment using flow cytometry
- Cell-associated viral RNA in CD4⁺ T cells pre- and post-treatment

Site laboratory standardized protocols will guide the performance of all research assays.

NOTE: See Section 7.2.6 regarding collection of stored Plasma/PBMC for Immunology Studies for participants who discontinue ART or do not complete study treatment.

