8.2.4 Randomization

Participants are randomized to the study Arms, assigned a RID, and receive vaccine/placebo at Day 0. Study Arm assignment is double-blinded and all randomized participants will receive either vaccine or placebo. The administration of the vaccination or placebo designates Day 0 and the calculation of the remaining visits are identified by consecutive days starting with Day 0.

Vaccine and placebo product will be indistinguishable. Site and laboratory personnel and study participants will be blinded with respect to the allocation of vaccine or placebo. The randomization plan will be generated centrally by the study statisticians at the UNC CFAR using computer software, and will be kept concealed from the study personnel.

8.2.5 Participants randomized to receive study product and do not receive the vaccine/placebo or are withdrawn from the study after receipt of the vaccine (reference protocol sections 7.2 and 7.3) will be replaced and the RID re-assigned at the time of next eligible participant randomization. Study Un-blinding

Study un-blinding will occur following an independent SMC review commencing approximately 28 days after the last participant receives their vaccine/placebo injection and completes the 2nd leukapheresis.

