Screening lab evaluation includes electrolytes (sodium, chloride, potassium, CO₂/bicarbonate), glucose, blood urea nitrogen (BUN), creatinine, calcium, phosphate, albumin, magnesium, LDH, and total protein in real time at the local laboratory.

Safety lab evaluations throughout the study include electrolytes (sodium, potassium, chloride, CO₂/bicarbonate), BUN, creatinine, calcium, magnesium, and glucose (also reference Pre-Vaccine Safety Lab Assessment).

Creatinine and Creatinine Clearance

Creatinine clearance (eGFR) calculations will use the CKD-EPI equation. This calculation can be found at https://www.qxmd.com/calculate/calculator_251/egfr-using-ckd-epi

The creatinine clearance (eGFR) will be required for study enrollment eligibility. The study assesses serum creatinine level at all the safety lab checks and uses the serum creatinine value for toxicity grading and as confirmation to receive vaccine or placebo doses.

The creatinine clearance (eGFR) value reported as part of the lab report of serum creatinine level will be re-assessed and re-calculated if incidental finding indicates a value \geq Grade 3. The re-calculated value using the CKD-EPI equation will be used to determine the severity of the lab abnormality.

Pre-Vaccine Safety Lab Assessments

Participants will have a Pre-Dose Safety Lab Assessment completed at either Visit 2 or the leukapheresis and within the 10 days prior to the vaccine/placebo dosing visit. These safety lab results must be within the eligibility criteria parameters established for this study. Labs that fall outside the parameters can be repeated one time only to qualify the participant to proceed on study.

After repeat testing, any lab value that remains outside the guidelines but considered clinically non-significant and documented as such by the study clinical PI (or designee), must be reviewed and approved by the protocol and/or safety committee prior to the vaccination.

Serum and Point of Care (POCT) Urine Pregnancy Test: A negative serum pregnancy test (to rule out pregnancy) is required on all women at screening, and a negative urine pregnancy test on Day 0, regardless of documented procedures that prohibit pregnancy.

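### Exploratory endpoints 6 and 7 place Day 30 in the pre-vaccination baseline although the only dose is on Day 0; the baseline should be two named pre-dose samples

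*Combined protocol and SAP*

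**What the plan says.** Section 3, Tertiary/Exploratory endpoints 6 and 7, report the proportion of participants whose post-vaccination value (geometric mean of Days 28 and 56) is lower "compared to pre-vaccination (geometric mean of Day -45 and Day 30"). The baseline wording is identical in both.

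On dosing, Section 6.1.2 states: "All participants will receive a single vaccine/placebo administration on Day 0". Section 8.2.4 fixes the day count: "The administration of the vaccination or placebo designates Day 0". Section 4.1 says of the second, post-vaccine leukapheresis: "This procedure can be completed between Day 21 through Day 35". Before dosing, participants "undergo one leukapheresis procedure between Day -60 and Day 0" (Section 4.1).

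Section 8.1 ties the virologic measurements to the schedule: "Plasma and cryopreserved PBMC will be stored for analysis of low level viremia, T-cell specificity, phenotype and function, and virologic measurements per the SOE". In Section 1.3 the row "Plasma and PBMC for Immunologic and Virologic Studies" marks, as far as the damaged table shows, three pre-dose time points: Screening, Enrollment/Baseline (with leukapheresis) and Day 0.

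Section 9.3.5 gives proportion endpoints a two-sided binomial 95% confidence interval, and Section 9.3.10 log-transforms virologic measures. Neither restates the baseline.

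**The concern.** Day 30 falls 30 days after the only dose, inside the Day 21 to 35 window of the post-vaccine leukapheresis and two days after a nominal sample already in the post-vaccination mean. A baseline that includes it contains part of any effect it is meant to measure.

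Each participant is classed as decreased or not from this one comparison, and the text does not settle which samples it means. Endpoint 7 also carries some weight in the design: Section 4.2 cites total HIV DNA as one of two reasons for requiring at least two years of suppression. Under Section 9.2.1.4 all participants are unblinded once the last has completed Day 28 and the second leukapheresis. If the text is still uncorrected then, the baseline pair would be chosen with arms known.

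**Working it through.** The plan gives no power or effect figure for these endpoints, so there is none to reproduce.

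**Setup.** On the log scale, let a and b be two pre-dose samples, x28, x30 and x56 the later ones, with independent normal errors of equal SD s. A participant is decreased when the difference is below zero.

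- Two pre-dose samples: D1 = (x28 + x56)/2 − (a + b)/2
- Day 30 is the Day 28 draw: D2 = (x28 + x56)/2 − (a + x28)/2 = (x56 − a)/2
- Day 30 is a separate draw: D3 = (x28 + x56)/2 − (a + x30)/2

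In D2 the Day 28 value has zero weight.

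**Apparent size of a sustained fall f under D3.** The log change is halved, so the apparent fall is 1 − √(1 − f). For f = 20%, 30%, 50% this is 10.6%, 16.3%, 29.3%.

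**Reclassification with no true change (any s).** Var D1 = s², Var D2 = s²/2, Var D3 = s².

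- cov(D1, D2) = s²/2, so r = 0.5/√0.5 = 0.707. The signs disagree with probability arccos(0.707)/π = 0.250, or 7 × 0.250 = 1.8 participants of 7.
- cov(D1, D3) = 0.75s², so r = 0.75. The probability is arccos(0.75)/π = 0.230, or 1.6 of 7.

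**Proportion classed as decreased, sustained fall.** With d = −ln(1 − f), the probabilities are Φ(d/s) for D1, Φ(d/(s√2)) for D2 and Φ(d/(2s)) for D3. The falls and SDs are assumptions; neither is in the documents.

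| s | f | D1 | D2 | D3 |
|---|---|---|---|---|
| 0.3 | 20% | 0.771 | 0.701 | 0.645 |
| 0.3 | 30% | 0.883 | 0.800 | 0.724 |
| 0.3 | 50% | 0.989 | 0.949 | 0.876 |
| 0.5 | 20% | 0.672 | 0.624 | 0.588 |
| 0.5 | 30% | 0.762 | 0.693 | 0.639 |
| 0.5 | 50% | 0.917 | 0.836 | 0.756 |

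The loss against D1 is 4 to 8 points for D2 and 8 to 16 for D3.

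**Other time courses, same assumed range.**

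- Fall gone by Day 56: D2 and D3 both give 0.500, which is chance, against 0.588 to 0.876 for D1. The loss is 9 to 38 points.
- Fall only at Day 56: D2 is 4 to 8 points higher than D1, and D3 equals D1. The error is therefore not always a loss.

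**Does Day -30 settle it?** It removes the contamination but does not identify the samples. Pre-dose safety labs are "completed at either Visit 2 or the leukapheresis and within the 10 days prior to the vaccine/placebo dosing visit" (Section 8.2.11). When Visit 2 and the leukapheresis share a day, that day therefore falls within 10 days of dosing. Screening is then the only plasma/PBMC draw before Day -10, and Day -45 and Day -30 cannot both be filled. Table 11 shows no other pre-dose blood visit except the optional lymph node aspiration.

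**The case against.** The strongest reply is that this is a dropped minus sign, in the source or in conversion of the file to text. The label says pre-vaccination and a separate post-vaccination mean is defined, so an analyst would be unlikely to use a Day 30 sample as baseline, and every figure above applies only to that literal reading. This is plausible. Loss in conversion is less likely, because the phrase occurs twice with the minus on Day -45 intact. In either case the samples still have to be named.

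The scheduling argument is also limited. If the leukapheresis is on a separate day, footnote 1 of Section 1.3 ties it, rather than Visit 2, to the 10 days before Day 0. Screening near Day -45 and Visit 2 near Day -30 could then both occur. That stands: the pair is not uniformly available, rather than never available.

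Finally, the consequence is modest. These are two exploratory endpoints in a 24-person pilot. Section 9.3.9 lists individual data by measure and time point, so another pair can be recomputed. At n = 7 the exact 95% intervals for 6/7 (42% to 99.6%) and 5/7 (29% to 96%) largely overlap. All of this stands. It limits the importance of the point but does not make the definition usable as written.

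**Conclusion.** The concern holds. As written, the baseline of endpoints 6 and 7 includes a post-vaccination time point, and nothing elsewhere in the plan overrides it. If applied literally, it either discards Day 28 or halves a sustained change on the log scale. With no true change it reclassifies 25% or 23% of participants relative to a two-sample pre-dose baseline; those percentages need only independent normal errors of equal variance. The 4 to 16 point losses for a sustained fall also rest on assumed falls of 20% to 50% and a within-person log SD of 0.3 to 0.5, and are illustrative. Under a Day -30 reading none of these effects arises, but the pair is still not tied to named draws. It should be corrected; safety and the secondary T-cell endpoints are untouched.

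**What to change.** Before unblinding, the sponsor should confirm which pair was intended and restate the baseline of both endpoints as the geometric mean of two named pre-dose samples, the same two for every participant.

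One workable pair is the baseline leukapheresis product and the Day 0 draw. Section 8.2.3 describes the first as the source of cells for baseline research assays, and under Section 7.2 participants without an adequate collection leave the study before dosing. Section 8.2.7 has the second taken before the injection. If another pair was meant, such as Day -45 and Day -30, name the two scheduled draws that supply it. Days 28 and 56 stay as the post-vaccination samples.

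The same edit should name the draw behind Day -60 in endpoint 5, which is not a named visit in the visible schedule, although it is not post-vaccination.

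The cost is one line in Section 3 for each endpoint. The samples are already scheduled, and the next full amendment foreseen in Letter of Amendment #1 could carry the change if it precedes unblinding.

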4 STUDY DESIGN

4.1 Overall Design

This is a Phase 1, single site, pilot study to evaluate the safety and immunogenicity of the **M3** and **M4** vaccines administered alone or in combination in HIV-infected participants suppressed on ART.

This is a double blind, randomized, placebo-controlled, parallel design study to evaluate the safety and immunogenicity of viral-vector, MVA, expressing immunogens, tHIVconsV3 (**M3**) and tHIVconsV4 (**M4**), derived from conserved yet immunogenic regions of HIV-1. The participant population is HIV-1 infected adults suppressed on ART with plasma HIV-1 RNA <50 copies/mL.

We hypothesize that the administration of **M3** or **M4** or **M3+M4** together will be safe in HIV-1-infected participants suppressed on ART. We hypothesize that the simultaneous administration of **M3** with **M4** (**M3+M4**) will result in both an increase in total magnitude

of HIV-1-specific T cell responses and increase the breadth of T cells targeting conserved regions of HIV-1 compared with either **M3** or **M4** vaccination alone.

We will administer vaccine and placebo doses to all participants as an IM injection in the deltoid muscle of the non-dominant arm, unless a participant requests vaccination in their dominant arm. Participants continue their baseline ART regimen throughout the study.

Randomized assignment 7:7:7:3 occurs at Day 0 to one of four arms as provided in [Table 6](#).

Table 6 Randomized Assignment

Arm	N	Day	Treatment	Dose (pfu)	Route
1	7	0	M3	2×10^8	IM
2	7	0	M4	2×10^8	IM
3	7	0	M3+M4	1×10^8 , each vaccine	IM
4	3	0	Placebo/saline	-	IM

M3 = MVA.tHIVconsV3

M4 = MVA.tHIVconsV4

pfu = plaque forming units

IM = intramuscular

The primary safety outcome is the occurrence of at least one \geq Grade 3 Adverse Event (AE) including signs/symptoms, lab toxicities, and/or clinical events that are possibly, probably, or definitely related to study treatment through 28 days following vaccination. The primary safety analysis will be blinded through Day 28 after the last dose of vaccine/placebo and the second leukapheresis is completed by the last participant.

Screening, Enrollment, and Leukapheresis. The participant reviews and signs the informed consent (ICF). Participants meeting eligibility requirements enroll and undergo one leukapheresis procedure between Day -60 and Day 0. The leukapheresis procedure collects white blood cells allowing for completion of detailed immunologic and virologic assays with minimal blood loss. Participants have the option to consent to a lymph node FNA; participants choosing this option will complete the pre-vaccine FNA between Day -60 and Day 0 and a post-vaccine FNA between Day 7 and Day 21. The post-vaccine FNA should be collected even if the pre-vaccine collection attempt is unsuccessful.

Randomization, Study Treatment, Follow-up Assessment, and Leukapheresis.

Randomization occurs at Day 0 when a randomization identification number (RID) will be assigned. All participants receive a vaccine or placebo dose as an IM injection. Post

vaccination safety assessments occur via clinical evaluations, and lab testing/evaluations. The study will collect research assays at designated visits.

At Day 28, all participants will undergo their 2nd leukapheresis. This procedure can be completed between Day 21 through Day 35. The leukapheresis product will be used for immunologic and virologic research assays post vaccine/placebo. Participants will be followed for immunogenicity assessments through Day 70 and safety assessments through Day 168 (Week 24) following the administration of vaccine/placebo at Day 0.

Note: The post-vaccine leukapheresis must be done as close to Day 28 as possible. There may be a rare situation where the completion of the procedure in the 2-week visit window will not be possible. As soon as the study coordinator becomes aware of this scenario, they should notify the study PI (or designee) to schedule the procedure outside the study window, preferably earlier (between Days 14 and 28). If the procedure can only be done after Day 35, participants should complete the Day 28 visit with collection of a 42.5 mL ACD sample at that visit.

